### I. Background and Significance

Digital pills provide real-time verification of medication ingestion events and can be used to monitor medication adherence; previous studies have demonstrated their acceptability in real-world patient populations. Digital pills comprise a radiofrequency emitter combined with a standard gelatin capsule that is compounded with a study medication. Upon ingestion of the digital pill, the chloride ion gradient in the stomach energizes the radiofrequency emitter, transmitting a unique signal of medication ingestion that is captured by a wearable Reader. The Reader acts as a relay, storing and transmitting ingestion data to a smartphone and cloud based server. Ingestion data is then available for real time interpretation by clinicians. Digital pill technology has been previously applied to opioid ingestion, diabetes management, and as a surrogate for directly observe therapy in schizophrenics.

Direct measures of medication adherence are an important advance in the study of medication adherence, especially among patients with poor adherence linked to substance use disorder. Although recent studies have demonstrated pre-exposure prophylaxis (PrEP) with once daily Truvada is efficacious in preventing HIV infection, protection is highly dependent on adherence. There is a clear dose response relationship between PrEP adherence and prevention of HIV transmission. Post-hoc analyses of the iPrEX data (corroborated by the PROUD and iPERGAY studies) found that individuals whose drug levels were consistent with taking 4 or more doses of TDF/FTC a week had a greater than 90% level of protection from HIV; but only 50% of MSM in iPrEX achieved consistent adherence. Substance use among MSM occurs syndemically in the context of other mental health vulnerabilities (most notably depression, sexual trauma, and intimate partner violence that increase their risk for condomless anal sex and HIV infection). Similarly, among HIV-infected MSM, the impact of substance use on ART adherence and HIV treatment outcomes is also well established and recent studies have already identified substance use as a significant barrier to optimal PrEP adherence among MSM.

### II. Specific Aims

**Aim 1: Technology Optimization.** To optimize the acceptability of DigiPrEP among MSM or transgender individuals with self-reported substance use through individual interviews (N=30);

**Aim 2: Technology Deployment.** To deploy DigiPrEP in MSM with self-reported substance use who are on PrEP (N=15) in a 90-day open label, proof-of-concept trial; and

**Aim 3: Technology Evaluation.** To evaluate the user response and primary care physician response to using DigiPrEP in the real-world through qualitative interviews.

### III. Subject Selection

Aim 1 Inclusion Criteria: 

1. MSM (cisgender male)

2. Self-reported use of non-alcohol substances of abuse in past 6 months

3. On PrEP or qualifies for PrEP

4. Age 18 or older

	Aim 1 Exclusion Criteria: 

1. Does not speak English

2. HIV positive

---	--

Aim 2 Inclusion Criteria:
 
 
1. MSM (cisgender male)
 
2. Self-reported use of non-alcohol substances of abuse in past 6 months
 
3. Currently taking PrEP
 
4. Has qualifying laboratory tests (Cr, hepatitis B immunization, STI testing and syphilis)
 
5. Age 18 or older
 
	
Aim 2 Exclusion Criteria:
 
 
1. Does not speak English
 
2. HIV positive
 
3. Identifies as transgender
 
4. Estimated creatinine clearance <60ml/min
 
5. Active hepatitis B treatment
 
6. Does not own a smartphone
 
7. Taking proton pump inhibitors
 
8. History of Crohn's disease or ulcerative colitis
 
9. History of bowel surgery, gastric bypass, bowel stricture
 
10. History of GI malignancy or radiation to abdomen
 
11. Unable/unwilling to ingest digital pill
 

Aim 3 Inclusion Criteria:
 
 
1. Participants in Aim 2 will be enrolled in Aim 3.
 
	
Aim 3 Exclusion Criteria:
 
 
1. Did not participate in Aim 2.
 

Due to the exploratory nature of this proposal, we will enroll only MSM individuals (cisgender male) in this study with the intent of generating preliminary data on feasibility of the digital pill in order to conduct future studies with transgender men and women.

#### IV. Subject Enrollment

For all aims of this study, we will publicize the study at Fenway Health primary care provider (PCP) meetings.

##### Recruitment of Fenway Patients

Aim 1: We will advertise the study through monthly research meetings at The Fenway Institute, and we will ask Fenway Health primary care physicians and other Fenway Health clinicians to refer patients to us. Potential participants will also be screened during clinical appointments at Fenway Health by study staff. New patients at Fenway Health are given a Notice of Privacy Practices which informs them that their protected health information may be utilized for research when the research proposal is IRB-approved and conducted in accordance with HIPAA privacy and confidentiality rules. Further, under HIPAA, as employees of the covered entity (Fenway Health), the study staff may utilize medical records to identify potential participants. Potentially eligible patients will be identified using crystal reports. A study staff member will then work with medical assistants and/or providers before approaching patients to assess interest. After entering the room and prior to screening, the study staff member will explain the study before asking permission to complete the screening questionnaire. Those who appear to be eligible will be invited to participate in the study after their appointment, or set up an appointment in the future. We will also post flyers and cards advertising the study at Fenway Health and throughout the greater Boston area, as well as via social media platforms (Grindr, Scruff, Growler, and Facebook). Participants who are interested in the study will call the RA and undergo a phone screen to ensure they meet enrollment criteria prior to being scheduled for a study visit.

Aim 2/3: We will utilize chart review, as well as screening during clinical appointments at Fenway Health (as described above) to identify HIV negative MSM with a history of substance use disorder who have qualifying laboratory evidence and are prescribed PrEP at Fenway Health. We will also identify potential participants through posted flyers in the greater Boston area, email blasts from the Fenway Health recruitment team, and social media advertisements. Email blasts from the Fenway Health recruitment team are received by patients and general public who sign up to receive general emails from Fenway Health regarding its daily operations, events and research studies. If applicable, we will inform their treating clinicians that their patient might be eligible for the study. The clinician will tell the patient about the study and acquire permission from the patient for study staff to speak with them at their next regularly scheduled clinic appointment or provide them with contact information for the study team. We otherwise will utilize crystal reports using our HIPAA Waiver to

screen potential Fenway Health participants, and approach them on the medical floors after consultation with the medical team. If potential participants are interested in the study after a discussion with their primary care physician, we will arrange a time to contact the participant and discuss the study in further detail. We will schedule an appointment with the study staff to discuss DigiPrEP. If participants enroll in the study, we will have them sign a medical release of information form to notify their treating clinician at Fenway Health about their participation. Additionally, we will ask participants in Aim 1 if they would be willing to participate in Aims 2/3. Participants who are interested in the study can respond to posted flyers, recruitment emails, or social media advertisements will call the RA and undergo a phone screen to ensure they meet enrollment criteria prior to being scheduled for a study visit.

### **Passive Recruitment**

We will also post flyers and cards advertising the study at Fenway Health and throughout the greater Boston area, and engage in recruitment via social media platforms (Grindr, Scruff, Growler, and Facebook) in order to extend our reach to as many potentially eligible individuals as possible. Participants who are interested in the study will call or email the RA and undergo a preliminary phone screen to ensure they meet basic enrollment criteria prior to being scheduled for a study visit.

### **Shared Cross-study Recruitment**

As potential participants are screened for DigiPrEP, they may additionally be eligible for a parallel study that is testing the use of the digital pill for PrEP adherence linked to a smartphone behavioral intervention in MSM with moderate to severe stimulant use disorder (PrEPSteps- IRB 1162312). While screening participants, if their schedules do not allow them to participate in DigiPrEP, but they indicate willingness to participate in other Fenway Studies, we will discuss the PrEPSteps study with them as described in our cross study screener. Participants who would benefit from learning about their PrEP adherence would likely also benefit from interventions that boost adherence as studied in PrEPSteps. We therefore will share screener data between the two studies in the case that participants also qualify for PrEPSteps and would like to participate. Both studies are conducted by the same PI and study coordinators.

## **V. Study Procedures**

Aim 1: In this aim, we will conduct individual interviews (see uploaded document *Aim 1 Interview*) of MSM with self-reported substance use currently on or qualifying for PrEP. Study participants will sign informed consent prior to the qualitative interview. An audio-recorded individual interview will be conducted by the RA or study investigator. We will explore the digital pill, acceptance of the technology, willingness to use technology for PrEP adherence and willingness to interact with the technology to reinforce adherence and address influencers of adherence. Interviews will be audio recorded, transcribed, and analyzed by the study team (see section VI), after that audio recordings will be destroyed. Participants will also complete a brief self-report questionnaire (see uploaded document (DigiPrEP\_selfreport\_questionnaire)). At the end of the visit, the participant will be remunerated via a \$40 gift card.

Aim 2/3: In Aims 2 and 3, we will deploy DigiPrEP in MSM who are already prescribed PrEP. This portion of the study will involve 5 study visits over the course of 3-4 months where participant ingest DigiPrEP daily. Participants will be prescreened via phone to assess initial eligibility for participation; if eligible, they will be scheduled for an in-person Screening Visit, where they will sign informed consent and full eligibility will be determined via rapid HIV test and review/conduct of necessary blood work. If determined to be eligible at the Screening Visit, participants will be scheduled for Study Visit 1; in the interim, a 90-day supply of digital pills will be ordered for shipment to the Fenway Pharmacy. At Study Visit 1, participants will be trained in the use of the digital pill and complete a self-report questionnaire (same questionnaire as in Aim 1). At Study Visit 2, we will dispense an additional 30-day supply of the digital pill, review adherence data with the participant, conduct a pill count of remaining pills, and conduct a blood draw for adherence. At Study Visit 3, we will dispense a final 30-day supply of the digital pill, review participant adherence data, and conduct a pill count of remaining pills. Following both Study Visits 2 and 3, we will also forward adherence data from the study visits to the participant's Fenway Health PCP, if applicable. At Study Visit 4, the final visit, we will review adherence data,

conduct a pill count of remaining pills, and conduct a blood draw for adherence. Additionally, as part of Aim 3, we will conduct a 20-minute semi-structured exit interview to assess participants' experiences in the study.

**Aim 2 – Prescreening:** Study participants prescreened on the phone who do not have a PCP at Fenway Health will be asked to bring their most recent copies of laboratory data to the in-person Screening Visit (chemistry or creatinine, evidence of hepatitis immunization status (within the past 6 months), sexually transmitted infection screening (STI) and syphilis screening (within the past 3 months)). If participants do not have qualifying laboratory tests, we will notify the participant that we will conduct any needed laboratory testing at the Screening Visit. We will send participants an email with a list of labs they should bring as part of the reminder for the Screening Visit.

**Aim 2 – Screening Visit:** This is the first study visit. During this visit, the participant will meet the RAs and study team. We will explain the course of the study, obtain written informed consent, and obtain a signed medical release of information form and completed locator form from participants. During the informed consent process, we will ask if participants want us to relay adherence data from the digital pill to their PCP; if they opt in, we will send monthly adherence information to their PCP. After obtaining consent, we will conduct a rapid HIV test to ensure that participants are HIV negative. We will also review laboratory data with participants; if they did not bring lab results with them (or grant us access to lab results via an online patient portal, following signing of medical release form), we will call their PCP and confirm their eligibility for PrEP (see *DigiPrEP\_PCP\_communication\_script*). If participants are missing any required labs, they will receive those tests at this visit. If individuals screen positive for active hepatitis infection, or have creatinine clearance <60ml/min, they will be ineligible for the study and referred back to their PCP for continued medical care. Individuals who test positive for STIs will be referred to their PCP for treatment. If they do not have a PCP, they will be referred to HIV care or STI care at Fenway Health or Brigham and Women's Hospital. Once we have reviewed all required laboratory work, and confirmed HIV status as negative, we will schedule participants for Study Visit 1. Additionally, following this visit, and prior to Study Visit 1, we will order a 90-day supply of digital PrEP for eligible participants (process detailed below following description of study visit procedures).

**Aim 2 – Study Visit 1:** During Study Visit 1, participants will complete a baseline self-report questionnaire, and the study team will conduct a short training around operation of the digital pill system (i.e., digital pills, Reader device, and mobile application) and instruct participants on basic troubleshooting of the technology. We will also help participants to download the mobile application where their adherence data will be recorded and accessible, train them on how to use the app, and register them on the collaborator interfaces (iAssist and Nomi). Participants will be provided with a 30-day supply of digital PrEP (Truvada); participants will then ingest their first digital PrEP dose during the visit to demonstrate their understanding of how to operate the digital pill system and to ensure the technology is functioning properly. Participants will receive a brief reference guide (see *refguide*) with key contact information and basic information regarding the digital pill and Reader. Participants will be scheduled for Study Visit 2, which will occur a maximum of 30 days (i.e., 23-30 days) after Study Visit 1, in order to ensure that participants do not run out of digital pills prior to receiving a refill. We will contact study participants via text message on days 1, 2, 5, and 7 to ensure technology is functioning. Additionally, beginning one week after Study Visit 1, participants will receive brief weekly surveys through the Nomi interface asking them to self-report substance use and sexual activity (see *DigiPrEP Study Messages\_Participant Only*). At the end of Study Visit 1, participants will be remunerated via a \$25 check.

**Aim 2 – Study Visit 2:** We will contact participants on days 23, 25, and 29 to remind participants of their Study Visit 2 appointment. During this study visit, participants will have blood drawn via phlebotomy and placed on a blood spot card in order to assess PrEP adherence. De-identified specimens will be banked for future use in drug abuse screening. We will review digital pill adherence data with participants in Nomi and conduct a pill count to validate adherence data from the digital pill and Reader. We will review discordant counts, periods of Reader activity that suggest no use of the Reader device, and digital pill use with the participant. We will additionally review any potential nonadherent events detected by the digital pill with participants using timeline followback to gauge potential reasons for nonadherence. We will view the adherence interface with study participants and discuss events surrounding potential nonadherence events. We will record user responses to

each of these timeline followback events. We will also dispense an additional 30-day supply of digital pills to participants. We will schedule participants for Study Visit 3 prior to discharge, which will occur a maximum of 30 days (i.e., 23-30 days) after Study Visit 2. Participants will be reminded that we will pass their adherence data along to their PCP; participants will have the option of opting out of this mechanism at each study visit. At the end of Study Visit 2, the participant will be remunerated via a \$25 check.

**Aim 2 – Study Visit 3:** We will contact participants on days 53, 55, and 59 to remind them of their Study Visit 3 appointment. During this visit, we will review adherence data from the digital pill in Nomi, conduct pill counts with participants, address discordant counts and review reader activity with the participants and address any nonadherence events potentially linked to sexual activity or substance use. The participant will receive a final 30 day refill of digital pills and will be remunerated via a \$50 check.

**Aims 2/3 – Study Visit 4:** This is the final study visit. We will contact participants on days 83, 85 and 89 to remind participants of Study Visit 4, including a reminder to bring all DigiPrEP equipment to this visit to return to the study team. Participants will have blood drawn for adherence, and we will review adherence data from the digital pill in Nomi and conduct pill counts. Additionally, we will conduct a 20-minute semi-structured interview (see *Aim 3 Exit Interview*) to assess participants' experience working with DigiPrEP and participating in the study. Participants will be encouraged to return to their PCP for continued PrEP prescribing. If they do not have a provider who can continue to prescribe PrEP following the end of the study, we will refer them to a provider at Fenway Health or the Brigham and Women's Hospital infectious disease clinic. Participants will be remunerated a total of \$150 at the end of this visit (i.e., the planned \$75, as well as an additional \$75 for assistance finding and troubleshooting bugs in the mobile app, and for completion of all study procedures).

Participant contact: We will contact participants via text message at described times after study visits (see *DigiPrEP Study Messages\_Participant Only*). Additionally, if participants do not respond to text messages (e.g., technology check-ins at days 1, 2, 5, 7), or to study appointment reminders, we will contact them via phone, text, and/or email. If we do not detect digital pill ingestions for 48 hours (2 doses) or if there are more than 2 missed doses in a week, we will contact participants via phone, text, and/or email to understand if there are issues with operating the digital pill or if missed doses represent true medication nonadherence. If we are unable to reach participants, we will leave phone or text messages, and call participants back the next business day. We will also communicate information about the study, including required lab work documentation for the Screening Visit, to participants via email.

Drug procurement: Digital pills are procured from Curant Pharmacy (our collaborating pharmacy). Once participants sign informed consent during the Screening Visit, and we have confirmed qualifying laboratory work and eligibility, we will securely email a Drug Order Form to Curant. This order form will contain the following information, as required by Curant: (1) participant's name; (2) participant's date of birth; (3) participant study ID number; (4) participant's anticipated start date; (5) target drug delivery date; and (6) delivery information for pharmacist at Fenway Pharmacy. Following receipt of the Drug Order Form, Curant will FedEx 90 digital pills (three 30-day supplies) to the Fenway Pharmacy. Confirmation of shipment receipt will be documented in the DigiPrEP Pharmacy SOP binder. At Study Visits 1, 2, and 3, we will complete a Prescription Card that study staff will bring to the Fenway Pharmacy, who will sign out drug to us. If participants no-show during their study visit, we will return and sign back in drug to the Fenway Pharmacy. In the event that a participant drops out of the study and we have remaining drug assigned to them in the Fenway Pharmacy, we will securely email a Cancel Order Form to Curant, along with a new Drug Order Form, requesting the required number of replacement bottles of drug, and/or new participant labels (as applicable). Curant will mail new participant labels to place on existing bottles of drug, as well as any additional bottles of drug, as needed.

Study visit scheduling: We will schedule study visits as close to 30 days apart as possible. Recognizing that participants may have scheduling conflicts, we will seek to schedule participants for study visits 2, 3 and 4 within 7 days prior to the 30-day mark in order to prevent participants from running out of digital PrEP pills.

Participant messaging: Participants will receive standard SMS text messages, as well as notifications from the mobile application which receives their adherence data from the digital pill. Upon enrollment in Nomi and iAssist interfaces at Study Visit 1, participants will receive a welcome message, including a contact number for the DigiPrEP study team. Participants will receive three technology check-in messages during the first week using the digital pill (on days 2, 5, and 7); these messages will prompt participants to respond with “0” for “I need help with something,” or “1” for “Everything’s OK!” If participants text back “0,” the study team will contact the participant to assist them further. Beginning one week after Study Visit 1, participant will also receive an anonymous REDCap link to a brief weekly survey, asking them to self-report substance use and sexual activity for the past week. Participants will also receive text messages reminding them of upcoming study visits. Depending on messaging settings in the Nomi interface, participants may also receive app notifications for ingestion confirmations, as well as messages related to Reader battery life and confirmations of manually recorded ingestions (see *DigiPrEP Study Messages\_Participant Only* for detailed content and timing of all participant messaging).

Potential participant directly contacted study RA, referred by Fenway Health primary care physician, or identified via medical record review and screened during clinical appointment at Fenway Health

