## VI. Biostatistical Analysis

Aim 1: We will conduct qualitative analysis on individual interviews in aim 1 to elucidate themes of technology acceptance, design, and optimal timing and delivery of messaging.

Aim 2: We will calculate descriptive statistics regarding the degree of adherence collected from the digital pill. We will also calculate the accuracy of the digital pill in comparison to pill counts and validate ingestion data compared to dried blood spot data. Because this is a pilot, proof-of-concept study, we will not be powered to determine the degree of adherence the use of a digital pill alone confers upon study participants.

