## **IX. Data Monitoring and Quality Assurance**

We will review and monitor data from DigiPrEP for each study participant. At each study visit, participants will undergo pill counts to correlate adherence data from DigiPrEP, and calculate the accuracy of the digital pill to measure PrEP adherence. Any discrepancies between the digital pill and pill counts will be addressed in real time at each study visit with the participant. For each participant, we will also review signaling from the digital pill to the Reader with our industry collaborator (eTectRx) to ensure there are no errors in data transmission contribution to missed adherence events. If errors occur as a result of data transmission, we will annotate this on the ingestion data.

The study investigators will conduct QA to review data after half of the patients (N=7) of Aim 2/3 are enrolled to ensure that data is accurate and no errors have been made.

The principal investigator ([name]) will be responsible for monitoring adverse events during the study, but Drs. [name] and [name] will assume this responsibility in the event that [name] is unavailable. The role of the responsible person is 1) to identify the concern, 2) develop an appropriate response that involves consultation whenever possible to alleviate or minimize any adverse event, and 3) to ensure that the adverse event is reported in a timely manner to the responsible authority.

Participants will be monitored for occurrence of events defined as any undesirable experience or unanticipated benefit. Events may occur during recruitment, technology deployment, and qualitative interviewing. For example, a participant may become distressed when asked questions about substance abuse and its impact on PrEP adherence. Based upon previous research couched in technology among hidden populations, we anticipate that these effects will be minimal. The principal investigator will assess whether an undesirable experience occurred (adverse event) and will record details of all adverse events (death, life threatening illness, new serious or permanent disability) that occur. Should such an event occur, the principal investigator will report the event within 24 hours to the Fenway Institute IRB.

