DigiPrEP Statistical Analysis Plan

Official title: Feasibility and Acceptability of Digital Pills to Monitor PrEP Adherence in MSM With Substance Use

NCT number: NCT03842436

Document date: September 03, 2021

DigiPrEP Statistical Analysis Plan

Sociodemographics.

Descriptive statistics were calculated for selected variables.

Digital pill system (DPS) performance and engagement metrics.

To analyze the performance of the DPS, the ground truth of PrEP ingestion events were defined as the pill counts obtained each month (i.e., the number of unused pills returned, subtracted from the number of pills previously dispensed). The number of DPS-recorded ingestions – which included the number of both Reader-detected and manually-reported ingestions – was compared with the aggregate pill count at each monthly timepoint; this was defined as the overall performance metric for the DPS. The Reader-detected ingestions count was used to reflect the number of times the DPS was operated correctly. Successful DPS operation was defined as ingestion of a digital pill, proper use of the wearable Reader, and confirmation of the ingestion on both the Reader and the app.

Reader-detected ingestions and manually-reported ingestions that co-occurred within 30 minutes were identified and reconciled; these events likely represented episodes in which a digital pill was ingested, and the ingestion was detected by the Reader, but the participant elected to manually record the ingestion in-app because the Reader was not correctly paired to the smartphone or was delayed in detecting the ingestion. Additionally, several ingestions were manually reported due to a known programming error in the app early in the study. As such, two participants were instructed to manually log all ingestions until an app update was made available; ingestion data for these two individuals were downloaded from their Readers at the end of the study period, and all Reader-detected ingestions were reconciled with manually-reported ingestions.

Participant engagement with the DPS was measured by calculating the total number of DPS-recorded ingestions and comparing the number of monthly DPS-recorded ingestions across each month of the study period.

TFV-DP in DBS.

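### At Study Visits 2–4 nothing requires the pill count, which the SAP treats as ground truth, to be recorded before the digital record is reviewed, or the original count to be kept

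*Protocol*

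**What the plan says.** **Reference standard.** The SAP, under digital pill system performance, states that "the ground truth of PrEP ingestion events were defined as the pill counts obtained each month". It computes the count as pills dispensed minus unused pills returned. Comparing device-recorded ingestions with that count gives the overall performance metric. Protocol section VI agrees: "We will also calculate the accuracy of the digital pill in comparison to pill counts".

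**Visit procedures (protocol section V).** The count and the joint review of the record fall at the same visit:

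- Visit 2, overview: "review adherence data with the participant, conduct a pill count of remaining pills, and conduct a blood draw for adherence".
- Visit 2, detailed text: "We will review digital pill adherence data with participants in Nomi and conduct a pill count to validate adherence data". The next sentence adds a review of discordant counts.
- Visit 3, detailed text: "we will review adherence data from the digital pill in Nomi, conduct pill counts with participants, address discordant counts".
- Visit 4, detailed text: "we will review adherence data from the digital pill in Nomi and conduct pill counts".

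**Discrepancies.** Section IX states: "Any discrepancies between the digital pill and pill counts will be addressed in real time at each study visit with the participant".

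**Change control.** Under Data Entry Process in section IX, edits to ingestion data need agreement between the study team and the device company, approval by the principal investigator, and an audit trail. Neither document sets a corresponding rule for the pill count.

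**The concern.** A reference standard should be fixed without knowledge of the measurement it is used to judge. Here the counter and the participant may both have the device's number in front of them when the count is made, and a mismatch is talked through on the spot. Such a conversation can produce an explanation (pills left at home, pills lost) that changes the number accepted as taken. A count that happens to agree gives no occasion for that conversation.

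This is separate from editing of the digital record. That side has an audit trail, and locking it would leave the count just as open.

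At stake is the meaning of the main performance result. If the reference has moved towards the record, close agreement partly reflects the reconciliation and not only the device. A reader of the results could not tell, because nothing requires the unreconciled count to survive.

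**Working it through.** No figure in the plan depends on this point, so there is nothing to reproduce. The check is mainly textual, with simple arithmetic for scale.

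**1. Which visits.** The Screening Visit and Study Visit 1 have neither a pill count nor a review of a past record. The point concerns Study Visits 2, 3 and 4.

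**2. Is a sequence fixed?** Wherever a visit description lists both tasks, the review is named first: in the overview and the detailed text for all three visits, and in the flowchart for Visits 3 and 4. The Visit 2 flowchart box omits the count. But the tasks are joined by commas or by *and*, with no word of sequence. List order is also unreliable as time order. For Visit 2 the overview puts dispensing first and the blood draw last, while the detailed text puts the blood draw first and dispensing near the end. The text therefore permits review before count, and does not prescribe it.

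**3. Is the count protected in some other way?** Neither document says that the counter is unaware of the record, that the count is recorded first, or that the original count is kept after discordance is discussed.

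**4. Who can know the record before the visit?** Participants can see their data in the app (Study Visit 1 text). Staff follow detections and make contact after 48 hours without one, or after more than 2 missed doses in a week (Participant contact text). So the lack of protection does not depend on the order of tasks within the visit.

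**5. Scale.** Let *r* be the recorded ingestions and *n* the pill count for one participant-month. Agreement is *r/n*. Lowering the count by one pill changes it by

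*r*/(*n* − 1) − *r*/*n* = *r*/[*n*(*n* − 1)],

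which equals 1/*n* when the change closes a one-pill gap (*r* = *n* − 1). Visits are 23 to 30 days apart, so with daily dosing *n* is about 23 to 30:

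- *n* = 30: 1/30 = 3.3 percentage points
- *n* = 23: 1/23 = 4.3 percentage points

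Illustration with assumed values: 25 by count and 20 recorded give 20/25 = 80%. If two of the five discordant pills are resolved by changing the count, 20/23 = 87%.

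The SAP compares against the aggregate count at each month. If that means pooling over the 15 planned participants, the monthly denominator is about 15 × 23 = 345 to 15 × 30 = 450. One pill is then worth only 1/450 = 0.2% to 1/345 = 0.3%. A shift of several points would need about one changed pill per participant. Over the study there are at most 15 × 3 = 45 participant-months.

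**6. What cannot be computed.** The documents give no counting error, no frequency of discordance and no rule for correcting a count. The actual effect on agreement cannot be derived.

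**The case against.** **No count is said to change.** Neither document says that a count is redone, adjusted or overwritten. The SAP formula has no term for explanations. The corrections that are described apply to the digital record, and the visit discussion is tied to Reader use and reasons for nonadherence. This stands as far as it goes: bias is possible, not shown. It does not close the gap, since nothing requires the original count to be kept.

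**Adjustment may improve the reference.** If two pills really were left at home, the raw count is wrong and 20/23 is the better figure in the illustration. This stands. It is why the adjusted count should be reported too, and why the direction of error cannot be asserted.

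**Counting first does not blind anyone.** The app and the between-visit monitoring give both parties prior knowledge, and the participant chooses which pills to bring back. This also stands. Recording first protects the recorded number from the visit discussion. It does not give full blinding.

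**The stakes are modest.** Counting capsules is fairly objective, the study is a 15-person proof of concept with a largely descriptive analysis, and the dried blood spot comparison cannot be altered by a conversation. This limits the severity. However, drug concentration, cut at a level standing for at least four doses a week, does not replace a pill-by-pill reference for device performance.

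**Conclusion.** The concern holds in a limited form. At Study Visits 2–4 the SAP's ground truth is obtained at the same visit as the joint review of the record it judges. Discordance is discussed with the participant, and neither recording the count first nor retaining the original is required. The reference is therefore not protected from the record. If counts were moved towards the record, agreement would be overstated, by an amount the documents do not allow one to derive. The 3.3 to 4.3 points per pill in a participant-month is a sensitivity, not an estimate of bias.

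Three stronger readings do not follow:

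- *The protocol schedules the review before the count.* This rests on word order alone, and the order of other tasks differs between the two descriptions of Visit 2.
- *Errors are corrected in one direction only, so accuracy is overstated.* No recount or correction rule is documented, and an adjustment could make the count more accurate.
- *Every visit is affected.* Only Study Visits 2, 3 and 4 are.

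The point should be acted on because the protection is nearly free and the metric rests on this count. It does not undermine the study.

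**What to change.** **Protocol, Visits 2, 3 and 4 (overview, detailed text and flowchart).** State that staff count the returned pills and enter the number with a time stamp in REDCap before Nomi is opened. Add the count to the Visit 2 flowchart box, where it is missing. Record any explanation of discordance, such as pills left at home or lost, in a separate field that does not overwrite the count.

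**SAP.** Define the primary performance metric on the original count (dispensed minus returned). Add a sensitivity analysis using explanation-adjusted counts, so that a raw count that was genuinely wrong is not locked in. Report both.

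**Data already collected.** The SAP is written largely in the past tense. It should state whether original counts were kept and which counts were analysed. If originals were not kept, say so as a limitation of the agreement result.

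**Limitation to state.** This does not remove what participants know from the app or what staff know from monitoring between visits.

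**Cost.** One or two data fields, a reordering of existing visit tasks and one extra analysis. No added staff or procedures.
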